## **12.2 Derived and transformed data**

Baseline will be considered to be the latest value obtained before study drug administration (eg Day 1, pre-dose; or Day –1 if not recorded at pre-dose; or screening if not recorded at pre-dose or on Day –1).

Laboratory data will be reported in standard units. Out-of-range laboratory tests may be repeated. If a test is out of-range at baseline and repeated before dosing, the latest repeat value before dosing will be used as baseline. However, if a test is out-of-range and repeated at any other time during the study, the out-of-range value (not the repeat value) will be included in statistical summaries.

TriPLICATE ECG and vital sign measurements will be made at screening and the mean of the three measurements for each subject will be used for analysis.

TriPLICATE PBMC measurements will be made and the mean of the three measurements for each subject will be used for analysis.

The PK parameters to be derived are given in Appendix B: Pharmacokinetic analysis.

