9.1 Planned number of subjects

Up to 12 healthy volunteers, excluding replacements

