13. Full physical and neurological examinations will be done at screening and at the follow-up visit. Brief (symptom-directed) physical examinations will be done at all other timepoints.
14. FSH tests in post-menopausal women (screening only).
15. Weight only at screening visit 2 (MRI; PET subjects only).
16. Vital signs consist of seated systolic and diastolic blood pressure, pulse rate, tympanic temperature, and respiratory rate. Vital signs will be done at the following timepoints.
 - *PBMC-only subjects*: screening; Day -1; predose and at 2, 4, 8, and 12 h postdose on Day 1; before dosing on Days 2–13; before, and at 2, 4, 8, and 12 h after dosing on Day 14; at 24 h (Day 15), 48 h (Day 16), 72 h (Day 17), 96 h (Day 18), 120 h (Day 19), and 144 h (Day 20) after the last dose of ASN51; and at follow-up
 - *PET subjects* will have the same timepoints as PBMC-only subjects, plus additional assessments at: imaging session 1 (baseline) and imaging session 3 (if held on Day 22 or Day 23)TriPLICATE measurements (obtained \geq 5 min apart) will be made at screening. Single measurements will be made at all other timepoints. Measurements should begin with subjects in a seated position, after resting for at least 5 min. Additional unscheduled assessments may be done at the discretion of the investigator. Morning vital signs should always be taken before study drug administration.
17. During the period of residence, ECGs will be recorded at the following timepoints.
 - *PBMC-only subjects*: screening; Day -1; predose and at 2, 4, 8, and 12 h postdose on Day 1; before dosing on Days 2–13; before, and at 2, 4, 8, and 12 h after dosing on Day 14; at 24 h (Day 15), 48 h (Day 16), 72 h (Day 17), 96 h (Day 18), 120 h (Day 19), and 144 h (Day 20) after the last dose of ASN51; and at follow-up
 - *PET subjects* will have the same timepoints as PBMC-only subjects, plus additional assessments at: imaging session 1 (baseline) and imaging session 3 (if held on Day 22 or Day 23)TriPLICATE recordings (obtained \geq 5 min apart) will be made at screening. Single recordings will be done at all other time points. Recordings should be made with subjects in a supine position, after resting for 5 min.

18. Laboratory safety tests consist of haematology, clinical chemistry, coagulation, and urinalysis. Samples are to be taken at screening, Day -1, before dosing on Days 8 and 14, on Day 20, and at follow-up. Samples for clinical chemistry only are to be taken at Imaging session 1.

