16.2.4 General considerations for data analyses

The minimum set of summary statistics for numeric variables will be: n, mean, standard deviation (or standard error), median, minimum, and maximum. 95% confidence intervals (CI) will be presented where appropriate for data interpretation.

Categorical data will be summarised in frequency tables with n and percentage. Summaries of a categorical variable will include all recorded values.

The minimum and maximum values will be presented to the same number of decimal places as the raw data collected on the CRF (or to 3 significant figures for derived parameters). The mean, median and percentiles (eg Q1, and Q3) will be presented to one additional decimal place. The standard deviation (SD) and standard error will be presented to 2 additional decimal places.

‘Baseline’ will be the latest value obtained before IMP administration (predose on Day 1, or Day –1 if not recorded at predose, or screening if not recorded at predose or on Day –1). Out-of-range laboratory tests may be repeated. If a test is out-of-range at baseline and repeated before dosing, the latest repeat value before dosing will be used as baseline. However, if a test is out-of-range and repeated at any other time during the study, the out-of-range value (not the repeat value) will be included in statistical summaries.

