## 5 Study design

This is a phase 1, open-label, dose escalation, PET study to investigate the brain occupancy of O-GlcNAcase, and the PD response in PBMCs, after repeated doses of ASN51 in healthy subjects.

Enrolment of up to 12 healthy subjects is planned, in up to 2 groups (Groups 1 and 2). Each group will consist of up to 6 subjects.

All subjects will receive once-daily (QD) doses of ASN51, by mouth, for 14 days: Group 1 will receive [REDACTED] ASN51 QD and Group 2 will receive [REDACTED] ASN51 QD. Group 2 will proceed only if the safety and tolerability of the previous dose level are acceptable, and the plasma concentrations of ASN51 are predicted to remain below the toxicokinetic limit, as determined by the Safety Review Group (SRG; see protocol section 8.5).

On Day 11, to evaluate the effect of food on PBMC response, subjects will receive ASN51 in the fed state following a United States Food and Drug Administration (FDA) high-fat breakfast. Subject fasting requirements are further detailed in protocol section 11.

In each group, 2 subjects will have a PBMC-only study design (section 5.1.1) and 4 will have a PBMC and PET scanning study design (section 5.1.2).

Schematic diagrams of each study design are in protocol section 8.2.

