### Template T\_LB1

Table 14.3.4.xx Summary of laboratory values outside the reference range by treatment and planned relative time

Laboratory Test (units)	Treatment	Planned Relative Time	n	H	L
	Treatment 1 (N=xx)				

Source: Listing 16.2.xx

H = Above reference interval, L = Below reference interval

*Programming notes: Continued with all tests, treatment groups and time points. The summary is based on the reference ranges (most common ranges used)*

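### The laboratory repeat rule swaps out-of-range values at baseline only, which lowers the Day -1 out-of-range count in Table 14.3.4.1 relative to the post-dose rows even if ASN51 has no effect

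*SAP*

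**What the plan says.** SAP 12.2 makes repeats optional: "Out-of-range laboratory tests may be repeated". It then sets two rules. For a baseline test that is out of range and repeated before the first dose, "the latest repeat value before dosing will be used as baseline". For a test repeated at any other point, "the out-of-range value (not the repeat value) will be included in statistical summaries". Protocol 16.2.4 has the same pair of rules, the second reading "if a test is out-of-range and repeated at any other time during the study, the out-of-range value (not the repeat value) will be included".

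The laboratory schedule is in protocol 12.1, note 18: "Samples are to be taken at screening, Day -1, before dosing on Days 8 and 14, on Day 20, and at follow-up". PET subjects also have clinical chemistry at imaging session 1. No laboratory sample is planned for Day 1, so baseline is in practice Day -1.

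There is no control arm (SAP section 5): "All subjects will receive once-daily (QD) doses of ASN51, by mouth, for 14 days". SAP 14.5 has out-of-range data summarised as well as listed. The output concerned is Table 14.3.4.1, titled "Summary of laboratory values outside the reference range by treatment and planned relative time". Its template (T_LB1) gives high and low counts by test, treatment and time point.

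**The concern.** A value just outside a reference limit tends to fall back inside when measured again, drug or no drug. The plan lets that happen at Day -1 and prevents it at Days 8, 14, 20 and follow-up. A reader going down the rows of Table 14.3.4.1 would therefore tend to see fewer flags at Day -1 than afterwards, with no placebo rows to show that the pattern comes from the rule.

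Repeats at Day -1 are foreseeable. Exclusion criterion 1 covers clinically relevant laboratory findings before the first dose, and criterion 21 expressly allows one repeat of ALT or AST to settle eligibility. Safety and tolerability is a secondary objective, so this table will be read for a signal.

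**Working it through.** The plan gives no expected out-of-range rate and no power calculation, so there is no figure of its own to reproduce. The check is a model with no drug effect.

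**Inputs from the documents**
- Up to 12 subjects, in two groups of up to 6 (protocol 8.1.1 and 9.1).
- 35 quantitative blood tests, counted from protocol Table 4: 19 chemistry + 13 haematology (including the five differential counts) + 3 coagulation.
- Values per visit: 35 × 12 = 420.

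**Assumptions (not in the documents)**
- p = 5%: chance that a first draw is out of range, equal at every visit (central 95% reference range, normal values).
- r = 0 to 1: fraction of out-of-range baselines that are repeated before dosing.
- Within-subject correlation 0.5 to 0.9.
- The repeat fills the Day -1 row of Table 14.3.4.1.

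**Formulas**
- q = probability that a repeat is still out of range, given that the first draw was. From 3 million simulated draws, q = 0.186, 0.333 and 0.594 at correlation 0.5, 0.7 and 0.9.
- Baseline rate under the plan = p × [1 − r × (1 − q)].
- Post-dose rate = p, because the first value stands.

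**Results at correlation 0.7**

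| r | Baseline rate | Post-dose rate | Post-dose / baseline | Baseline flags of 420 | Baseline flags per cell of 6 |
|---|---|---|---|---|---|
| 0 | 5.0% | 5.0% | 1.0 | 21 | 0.30 |
| 0.25 | 5 × (1 − 0.25 × 0.667) = 4.2% | 5.0% | 1.2 | 17.5 | 0.25 |
| 0.5 | 5 × (1 − 0.5 × 0.667) = 3.3% | 5.0% | 1.5 | 14 | 0.20 |
| 1 | 5 × (1 − 0.667) = 1.7% | 5.0% | 3.0 | 7 | 0.10 |

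Post-dose, the expected counts are 420 × 0.05 = 21 per visit and 6 × 0.05 = 0.30 per cell. The largest per-cell shortfall at this correlation is 0.30 − 0.10 = 0.20 of a subject.

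**Other correlations, all out-of-range baselines repeated (r = 1)**
- 0.5: 5 × 0.186 = 0.9%.
- 0.9: 5 × 0.594 = 3.0%.

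**Mean change from baseline.** For a test flagged only above its upper limit, the upward bias is 0.003 to 0.04 SD over correlations 0.9 to 0.3 and r from 0.5 to 1.

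**One rule at all times (correlation 0.7, every out-of-range test repeated).** First value throughout: 5.0% before and 5.0% after dosing. Latest repeat throughout: 1.7% and 1.7%. Either removes the artefact.

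**The case against.** The rule has a rationale. Baseline is defined as the latest pre-dose value, and after dosing a reassuring repeat should not erase a possible safety signal. Both points stand, but neither requires the Day -1 row of an out-of-range count to follow a different rule from the rows beneath it.

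It can also be said that SAP 12.2 only makes the repeat the baseline and does not say that it fills the Day -1 row. SAP 12.1 keeps data from unscheduled time points out of summaries. That is a fair ambiguity. However, 12.2 sets the baseline rule directly against a rule about what enters the summaries, so replacement is the natural reading. If it is not what was meant, the SAP needs to say so.

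A reader might also infer more than the documents support:
- **That Day -1 is the only off-drug reference.** It is not. T_LB1 covers all time points. Screening, and imaging session 1 chemistry in PET subjects, come under the rule that keeps the first value. They help only in part, because eligibility selects the screening values.
- **That post-dose abnormalities are inflated.** They are not; each post-dose row shows the ordinary single-draw rate.
- **That habitual borderline values get reported as new on treatment.** No shift table or new-abnormality output is planned, and an abnormal result becomes an adverse event only under the criteria in protocol 14.2.
- **That Table 14.3.4.2 carries the same contrast.** Its template (T_LB3) has no time column, so it makes no before-and-after comparison.
- **That 21 baseline flags will fall to 7.** That needs every out-of-range baseline to be repeated, and it pools all tests and both groups, which no planned table does.

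**Conclusion.** The asymmetry is in the current text of both documents. Its direction is certain whenever some out-of-range baselines are repeated and some of those repeats come back in range: the Day -1 count in Table 14.3.4.1 is too low relative to the post-dose rows.

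The size cannot be fixed from the documents, because the out-of-range rate, repeat fraction and within-subject correlation are all assumed. Under the assumptions above it runs from nothing to a baseline rate of about one third of the post-dose rate at correlation 0.7. In any single cell of six subjects it is a fraction of a subject; it shows as a drift across many tests, not in one.

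It does not reach the conclusions that matter most. The comparison named in SAP section 10 is between doses and is unaffected if both groups are repeated alike. Mean changes move little. There are no hypothesis tests (SAP 4.3), so no error rate is involved. This is a modest, avoidable bias in one descriptive safety table.

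**What to change.** Add one sentence to SAP 12.2: Table 14.3.4.1 counts the first scheduled value at every visit, including Day -1; the latest pre-dose repeat remains the baseline for change from baseline; and all repeats are listed. Record this in SAP section 17 as a change from protocol 16.2.4. The sentence also settles how 12.1 and 12.2 fit together for the Day -1 row.

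No new data are needed. The Day -1 count may rise slightly and will include some values that a repeat did not confirm. A Day -1 value may also be flagged in Table 14.3.4.1 while the change-from-baseline tables (14.3.5.x) use an in-range repeat for the same subject and test. A footnote should say so.

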## **12.3 Assessment windows**

No assessment windows are defined for this report.

## 12.4 Vital signs reference ranges

The following vital signs ranges will be used:

Vital Sign	Range
Seated systolic blood pressure	90–140 mm Hg
Seated diastolic blood pressure	40–90 mm Hg
Seated pulse rate	40–100 beats/min
Tympanic temperature	35.5–37.8°C
Respiratory rate	10–16 breaths/min

## 13 Study population

### 13.1 Disposition of subjects

The disposition of all subjects in all populations will be summarised including: number of subjects by treatment; number completing the study, by treatment; and number withdrawn from the study. Screen failures will also be listed and summarised.

All subjects who withdraw or are withdrawn from the study will be listed, by treatment, with the reason for withdrawal.

A listing of analysis populations will be provided.

### 13.2 Protocol deviations

Before closing the database, data listings will be reviewed to identify any significant deviations and determine whether the data should be excluded from any analysis populations.

Major protocol deviations include subjects who:

- Entered the study even though they did not satisfy the entry criteria.
- Met the criteria for withdrawal from the study but were not withdrawn.
- Received the wrong treatment or incorrect dose.
- Received an excluded concomitant therapy.
- Received investigational product(s) past the expiration date.

In addition, subjects with minor time deviations (measurements taken outside the allowable windows) will be identified. Allowable time windows for pharmacokinetic samples and other procedures are given in 12.2 of the study protocol.

### **13.3 Demographic and baseline characteristics**

Demographic and baseline characteristics (eg physical examination, vital signs and ECGs) will be listed and summarised.

Subjects who take concomitant medication will be listed. All non-trial medication will be coded using the latest version of the World Health Organisation (WHO) ATC index (version 2021 or higher).

Medical and surgical history data will also be listed. Medical and surgical history will be coded using the version of the Medical Dictionary for Regulatory Activities (MedDRA) current at the time of database lock.

### **13.4 Treatment compliance**

Dates and times of dosing will be listed.

## **14 Safety analyses**

Summaries and listings of safety data will use the safety population.

### **14.1 Extent of exposure**

The dates and times of treatment dosing will be listed to indicate exposure to the study medication.

### **14.2 Adverse events**

AEs will be coded using the version of the Medical Dictionary for Regulatory Activities (MedDRA) which is current at the time of database lock (version 25.1 or higher).

All AEs will be listed.

The number of subjects with at least one treatment-emergent adverse event (TEAE) per treatment will be tabulated by actual treatment and MedDRA system organ class. A TEAE is defined as an event emerging during treatment (having been absent pre-treatment) or that worsens after treatment.

For each of the following, the number of TEAEs and the number of subjects with TEAEs will be summarised by treatment:

- TEAEs, by system organ class and preferred term
- Drug-related (“possibly”, “probably” or “definitely” as recorded by the investigator)

TEAEs, by system organ class and preferred term

Subjects with more than one TEAE will be counted only once, at the greatest severity or causality, for each system organ class/preferred term. Multiple TEAEs in a subject will be counted once per system organ class and preferred term. AEs with missing severity and/or causality will be treated as severe and definitely related, respectively.

Summaries will be sorted by system organ class and decreasing total incidence of preferred term.

### **14.3 Deaths, serious adverse events and other significant adverse events**

Deaths and serious adverse events (SAEs) will be listed separately (fatal events separate from non-fatal events). Other significant AEs, as identified by the investigator in the CRF, will be listed separately.

### **14.4 Adverse events leading to withdrawal from the study**

AEs leading to withdrawal will be listed separately.

### **14.5 Clinical laboratory evaluations**

Data from haematology, coagulation, urinalysis, and clinical chemistry will be summarised by treatment.

The laboratory tests with normal ranges that are different from the ranges most commonly used in the study (reference ranges) are listed in Appendix A: Laboratory tests with different ranges.

Data from haematology, coagulation, and clinical chemistry outside the normal ranges (used to assign clinical significance) and/or reference ranges (the most commonly used in the study) will be listed. Data outside the reference ranges will be summarised.

### **14.6 Other safety measures**

#### **14.6.1 Vital signs**

Vital signs evaluation at each planned assessment, and change in vital signs from baseline (Day 1, pre-dose) at each planned post baseline assessment, will be summarised by actual treatment.

Vital signs data outside of the normal range will be listed and summarised.

A separate listing of vital sign findings, classified as clinically significant by the investigator will also be provided.

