#### **14.6.2 ECG**

QT interval data will be presented using Fridericia's (QTcF) corrections.

ECG variables will be summarised by treatment and time point. Differences from baseline (Day 1 pre-dose) will be summarised by treatment and time point.

QTcF values > 450 msec, PR interval shortening < 110 msec, and PR interval prolongation > 220 msec, and increases of QTcF from baseline of > 30 msec and > 60 msec, will be listed by treatment and timepoint and summarised. A separate listing of ECG findings classified as abnormal by the investigator will also be provided.

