### Template T\_LB3

Table 14.3.4.xx Summary of laboratory values outside the reference range by treatment

Laboratory Test (units)	Treatment	m	H	L	Overall*
	Treatment 1 (N=xx)				

Source: Listing 16.2.xx

H = Above reference interval, L = Below reference interval

Subjects only counted once per treatment per category

\*Subjects only counted once per treatment

*m = total number of results for that parameter*

*Programming notes: Continued with all tests, treatment groups and time points. The summary is based on the reference ranges (most common ranges used)*

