### Template T\_VS2

Table 14.3.6.xx Summary of vital signs outside the normal range by treatment, planned relative time and parameter

Treatment	Planned Relative Time	Systolic Blood Pressure (mmHg)		Diastolic Blood Pressure (mmHg)		Heart Rate (beats/min)		Temperature (C)		etc	
		n	(%)	n	(%)	n	(%)	n	(%)	n	(%)
Treatment 1 (N=xx)	Time 1										
	Time 2										

Source: Listing 16.2.xx

*Programming notes: Continued with all treatments and parameters. n = total number of results for that parameter*

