**Template T\_VS3**

Table 14.3.6.xx Summary of Summary of vital signs outside the normal range by treatment and parameter (excluding baseline time point)

Treatment	Systolic Blood Pressure (mmHg)		Diastolic Blood Pressure (mmHg)		Heart Rate (beats/min)		Temperature (C)		etc	Overall*	
	n	(%)	n	(%)	n	(%)	n	(%)		n	(%)
Treatment 1 (N=xx)											

Source: Listing 16.2.xx

Subjects only counted once per treatment per parameter

\*Subjects only counted once per treatment

*Programming notes: Continued with all treatments and parameters. n = total number of results for that parameter. Only include post-treatment time points*

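### The out-of-range vital-sign tables pool low and high values, so opposite findings can print as the same count (minor, cheap to fix)

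*SAP*

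**What the plan says.** SAP 14.6.1, and protocol 16.2.6.3 in the same terms, commits to this: "Vital signs data outside of the normal range will be listed and summarised". Neither says whether low and high values are kept apart. The shells in SAP 19.2.1 settle it:

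- **T_VS2 (Table 14.3.6.2)**, titled "Summary of vital signs outside the normal range by treatment, planned relative time and parameter", has a single n (%) pair for each vital sign at each time point.
- **T_VS3 (Table 14.3.6.3)** has a single n (%) pair per vital sign over all post-treatment time points, plus an Overall column. Its footnote reads "Subjects only counted once per treatment per parameter".

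Neither shell has a high/low header or footnote. All five ranges in SAP 12.4 have a lower and an upper limit, for example "40–100 beats/min" for pulse and "10–16 breaths/min" for respiratory rate.

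Other safety tables in the same SAP keep direction:

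- **T_LB1** has separate columns, defined as "H = Above reference interval, L = Below reference interval".
- **T_LB3** has the same two columns with the counting rule "Subjects only counted once per treatment per category".
- **SAP 14.6.2** treats "PR interval shortening < 110 msec, and PR interval prolongation > 220 msec" as distinct findings, and T_EG3 has separate short and long PR columns. (T_EG3 prints a lower limit of 120 msec, not 110. That is a separate matter.)

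**The concern.** Tables 14.3.6.2 and 14.3.6.3 are the only planned tables that count out-of-range vital signs by dose. The trial has no control group, SAP 10 names the comparison between ascending doses as the one of interest, and vital signs are a listed secondary safety endpoint. A count that adds values below range to values above range cannot tell opposite findings apart. A group with hypotensive readings and a group with hypertensive readings can show the same number. A shift away from one limit and towards the other can leave the count where it was, or lower it. No reason is given for handling vital signs differently from laboratory tests and PR interval.

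**Working it through.** The plan states no figure on this point, so there is none to reproduce.

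**1. An example that needs no distribution.** Inputs: up to 6 subjects per group (SAP 5) and the T_VS3 counting rule. Suppose two Group 1 subjects have a systolic value above 140 mm Hg and two Group 2 subjects have one below 90 mm Hg. T_VS3 prints 2/6 = 33.3% for both doses. Split by direction, it would print L 0, H 2 against L 2, H 0.

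**2. A shift across the range.** Limits are from SAP 12.4. The documents give no means or SDs, so these are assumed, with normal distributions. With lower limit a, upper limit b, mean m and SD s:

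low = Φ((a − m)/s); high = 1 − Φ((b − m)/s); pooled = low + high.

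Systolic pressure, for instance, has limits 90 and 140. At mean 120, SD 10, low = Φ(−3) = 0.135%, high = 1 − Φ(2) = 2.275%, pooled 2.41%. At mean 110, low = Φ(−2) = 2.275%, high = 1 − Φ(3) = 0.135%, pooled 2.41%.

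| Vital sign (assumed SD) | Mean | Low | High | Pooled |
|---|---|---|---|---|
| Systolic (10) | 120 → 110 | 0.135% → 2.275% | 2.275% → 0.135% | 2.41% → 2.41% |
| Pulse (9) | 65 → 75 | 0.274% → 0.005% | 0.005% → 0.274% | 0.279% → 0.279% |
| Pulse (12) | 65 → 75 | 1.861% → 0.177% | 0.177% → 1.861% | 2.038% → 2.038% |
| Respiratory rate (2) | 12 → 14 | 15.87% → 2.28% | 2.28% → 15.87% | 18.14% → 18.14% |
| Respiratory rate (1.5) | 12 → 14 | 9.12% → 0.38% | 0.38% → 9.12% | 9.50% → 9.50% |
| Diastolic (9) | 75 → 65 | 0.005% → 0.274% | 4.779% → 0.274% | 4.784% → 0.547% |
| Pulse (10) | 50 → 65 | 15.87% → 0.62% | 0.00% → 0.02% | 15.87% → 0.64% |

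Small differences in the sums are rounding. The unchanged rows are those where the two means lie symmetrically about mid-range. In the last two rows the mean moves from nearer one limit to mid-range or closer to it, and the pooled rate falls although the other tail rises.

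**3. What this means in subjects and readings.** In T_VS2, at one time point with 6 subjects:

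- Systolic low: 6 × 0.135% = 0.008 → 6 × 2.275% = 0.14 expected subjects.
- Diastolic pooled: 6 × 4.784% = 0.29 → 6 × 0.547% = 0.03.
- Respiratory rate high (SD 2): 6 × 2.28% = 0.14 → 6 × 15.87% = 0.95.

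Over the whole study, protocol 12.1 note 16 gives 28 post-dose readings per subject: 4 (Day 1) + 12 (Days 2–13) + 1 + 4 (Day 14) + 6 (Days 15–20) + 1 (follow-up). That is 6 × 28 = 168 per group. If every reading came from the shifted distribution, the expected counts would be:

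- Systolic low: 168 × 2.275% = 3.8.
- Pulse high: 168 × 1.861% = 3.1 (SD 12) or 168 × 0.274% = 0.46 (SD 9).
- Diastolic low: 168 × 0.274% = 0.46.

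**4. Which table is affected, and how.** T_VS3 leaves out baseline, so pooling there affects only the comparison between doses. A before/after comparison of counts is possible only in T_VS2.

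**The case against.** The strongest reply is that direction is already reported elsewhere. Table 14.3.6.1 (shell T_VS1) gives mean, SD, median, minimum and maximum of each vital sign and of its change from baseline, by treatment and planned time. In the systolic example it would show a mean change of about −10 mm Hg, and the minimum and maximum show which limit was crossed. Individual plots are planned for systolic pressure, diastolic pressure and heart rate. Listing 16.2.9.1 prints the actual values, and clinically significant findings and complete data are also listed. With up to 6 subjects per group, these can be read by eye.

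This stands, and it limits the point. A reader might infer that a drug effect on vital signs would be missed, or would be reported as fewer abnormalities. The documents do not support that: the pooled counts do not stand alone, and the SAP nowhere assigns them the task of detecting a directional shift.

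Three further replies also have weight:

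- No decision depends on these tables. Protocol 8.4.1 bases trial stopping on adverse events, the Safety Review Group reviews vital signs before Group 2, and a physician reviews out-of-range values during the trial.
- The percentages rest on assumed distributions. Screening applies the same blood pressure and pulse limits, with a borderline allowance, so real pre-dose rates may be lower than modelled.
- The shells are partly illustrative. Both abbreviate the parameter list, and their notes define n as the number of results for the parameter.

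None of this explains why the vital-sign shells drop a distinction that the laboratory shells make. Temperature and respiratory rate also have no individual plots, so they depend more on the tables.

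**Conclusion.** The point holds as a minor defect in two safety tables. As specified, T_VS2 and T_VS3 pool values below and above two-sided ranges, against the SAP's own practice in T_LB1, T_LB3 and T_EG3. Opposite findings at the two doses can print as the same count in T_VS3, and a shift across the range can leave the T_VS2 count unchanged or lower. The first statement follows from the shells alone. The rates for the second are illustrations under assumed normal distributions, means and SDs, and most come to less than one expected subject per time point. No estimate is biased and no information is lost from the report. The evidence for pooling is the layout of the two shells, since the sentence in SAP 14.6.1 does not establish it.

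**What to change.** In T_VS2 and T_VS3, replace the single n (%) pair per vital sign with two, below range (L) and above range (H), and add the footnote already used in T_LB1. In T_VS3, count each subject once per direction, following the T_LB3 rule, and keep the existing Overall column. An L or H flag in place of the bare asterisk in Listing 16.2.9.1 is optional, because the listed value already shows direction. The change needs an edit to the SAP shells and minor programming. It needs no new data and no protocol change. The only drawback is wider tables.
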